8.2.1. Inclusion criteria

All pregnancies identified from 1 January 2005 through 31 December 2015 (both dates inclusive) in Denmark, Finland, and Norway and all pregnancies identified from 1 July 2006 through 31 December 2013 (both dates inclusive) in Sweden.

8.2.2. Exclusion criteria

Patients meeting any of the following criteria will not be included in the study:

1. Pregnancies with exposure to known teratogenic medications during the first trimester;
2. Pregnancies carrying a foetus with a chromosomal abnormality diagnosis.

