3. ABSTRACT

Protocol A0081359 Version 1.0 23 November 2018

Title: A Population-based Cohort Study of Pregabalin to Characterize Pregnancy Outcomes

Rationale and background: Pregabalin (Lyrica[®], Pfizer Limited) was approved in July 2004 by the European Medicines Agency (EMA) for the treatment of peripheral neuropathic pain and as an adjunctive therapy for adult patients with partial onset seizures. Subsequently the marketing authorizations were expanded to include the additional indications of generalized anxiety disorder (GAD) in March 2006 and central neuropathic pain in September 2006.

A recent study using data from eight European Teratology Information Services (TIS), based on 164 pregabalin-exposed and 656 pregabalin-unexposed pregnancies, reported an increased risk in non-chromosomal major birth defects associated with first-trimester pregabalin exposure. A subsequent study based on 477 pregabalin-exposed pregnancies among Medicaid beneficiaries in the United States (US) did not confirm the increased risk. Pfizer is therefore conducting this study to address this issue.

This non-interventional study is designated as a Post-Authorisation Safety Study (PASS) and is a commitment to the EMA.

Research question and objectives:

The study objectives are to describe the use of pregabalin exposure in pregnancy and to estimate the risk of major congenital malformations, birth outcomes other than congenital malformations and neurodevelopmental outcomes with the use of pregabalin.

The primary objectives of the study are to:

- Describe use of pregabalin, lamotrigine, and duloxetine during pregnancy by
 - overall (as used in women for any therapeutic use),
 - trimester,
 - indication,
 - cumulative dose
 - calendar year of delivery,
 - as both overall and in the subcategory of monotherapy (no concomitant administration with other antiepileptic drugs AEDs);
- Describe the prevalence of major congenital malformations after first-trimester in-utero exposure to pregabalin (yes/no); after first-trimester exposure to lamotrigine, after first-trimester exposure to duloxetine and after first-trimester exposure to lamotrigine or duloxetine;
- Estimate the association between first-trimester exposure to pregabalin and prevalence of major congenital malformations, as compared with no exposure to

- pregabalin; exposure to lamotrigine; exposure to duloxetine; and exposure to lamotrigine or duloxetine;

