7. RESEARCH QUESTION AND OBJECTIVES

The study objectives are to describe the use of pregabalin exposure in pregnancy and to estimate the risk of major congenital malformations, birth outcomes other than congenital malformations and neurodevelopmental outcomes with the use of pregabalin. Association between pregabalin exposure and a given safety outcome will be assessed for pregabalin exposure during a relevant gestational period using, alternatively, unexposed subjects and subjects exposed to treatments with indications similar to those of pregabalin (active comparators); effect exposure to pregabalin monotherapy will be assessed in a sensitivity analysis.

The specific primary objectives of the study are to:

- Describe use of pregabalin, lamotrigine, and duloxetine during pregnancy overall, by trimester and by calendar year of delivery in pregnancies ending in live or stillbirths, as characterized by
 - Prevalence of use (proportion of pregnancies with 1 or more dispensing of a given drug),
 - Distribution of therapeutic indications among the exposed pregnancies (epilepsy, GAD, neuropathic pain),
 - Cumulative dose, based on dispensings count and amount dispensed in each;
- Describe the prevalence of (proportion of live or stillborn children with) major congenital malformations after first-trimester in-utero exposure to pregabalin (yes/no); after first-trimester exposure to lamotrigine, after first-trimester exposure to duloxetine, after first-trimester exposure to lamotrigine or duloxetine, in pregnancies ending in live or still birth; in live or stillborn children unexposed to antiepileptics in the first trimester; and in the total population of live or stillborn children;
- Estimate the association between first-trimester exposure to pregabalin and prevalence of major congenital malformations, as compared with no first-trimester exposure to pregabalin, with first-trimester exposure to lamotrigine, with first-trimester exposure to duloxetine, and first-trimester exposure to lamotrigine or duloxetine, in live or stillborn children;
- Describe the prevalence of birth outcomes other than major congenital malformations (listed in [Section 8.3.2.1](#)) according to exposure (yes/no) to pregabalin any time

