8.3. Variables

8.3.1. Exposures

For the purposes of timing of exposure, trimesters of pregnancy will be defined as follows:

- First trimester: from the first day of the last menstrual period (LMP)-90 days to LMP+97 days (both dates inclusive);
- Second trimester: from LMP+98 days to LMP+202 days (both dates inclusive);
- Third trimester: from LMP+203 days (inclusive) until pregnancy end date (not included).

Exposure during the first trimester

Pregabalin exposure during the first trimester will be defined as at least one maternal dispensing of pregabalin during the first trimester. Pregabalin monotherapy in the first trimester will be defined as first-trimester exposure to pregabalin and no first-trimester dispensing for any other AED.

Comparators:

Unexposed to pregabalin during the first trimester comparator is defined as pregnancies without a dispensing for pregabalin or any other AED, including lamotrigine or duloxetine, during the first trimester.

Lamotrigine exposure in the first trimester is defined by at least one dispensing of lamotrigine during the first trimester. Lamotrigine monotherapy in the first trimester will be defined as first-trimester exposure to lamotrigine and no first-trimester dispensing for any other AED.

Duloxetine exposure in the first trimester is defined by at least one dispensing of duloxetine during the first trimester. Duloxetine monotherapy in the first trimester will be defined as first-trimester exposure to duloxetine and no first-trimester dispensing for any AED.

Lamotrigine or duloxetine exposure in the first trimester is defined by at least one dispensing of lamotrigine or duloxetine or both during the first trimester. Lamotrigine or duloxetine monotherapy in the first trimester will be defined as first-trimester dispensing of lamotrigine or duloxetine or both and no first-trimester dispensing for any other AED.

For analyses that use lamotrigine as the comparator, pregnancies exposed to both pregabalin and lamotrigine in the first trimester will be excluded. For analyses that use duloxetine as the comparator, pregnancies exposed to both pregabalin and duloxetine in the first trimester will be excluded.

Exposure any time during pregnancy

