8.7.4.1. Descriptive analysis

- Pregabalin use in pregnancy will be described as the number and proportion of pregnancies exposed in the first trimester, and in any trimester. Number and proportion of pregnancies with pregabalin monotherapy will be reported. Cumulative dose during first trimester and any trimester will be described based on the amount of dispensings during a relevant period. Use of lamotrigine and duloxetine will be similarly described.

- Distributions of the characteristics of the study population will be tabulated according to pregabalin exposure categories: first trimester (exposed/unexposed); any trimester (exposed/unexposed) and separately for the monotherapy subgroup. Categorical variables will be summarized using frequencies and proportions; continuous variables using either mean and standard deviation (SD), or median and interquartile range (IQR) as appropriate.
- Distribution of maternal and offspring characteristics in the study population will be tabulated according to pregabalin and the active comparator categories, as above. All descriptive tables will be constructed including stillbirths.
- Crude prevalence of the major congenital malformations will be reported according to first-trimester exposure to pregabalin (overall and in the subcategory of monotherapy) and each comparator (overall for all comparators including not exposed and in the subcategory of monotherapy for lamotrigine and duloxetine). In addition overall prevalence of malformations in the whole general population will be presented. Crude prevalence of the other birth outcomes (stillbirth, low birth weight, small for gestational age (SGA), preterm birth, low Apgar score at 5 minutes and microcephaly) will be reported according to any trimester exposure to pregabalin and each comparator, in the same fashion.

Major congenital malformation outcomes

Major congenital malformations (any, each major malformation type sample size permitting), among pregnancies ending in a live or a stillbirth pregnancies exposed to pregabalin during the first trimester will be compared against each of the comparators estimating crude and adjusted prevalence ratios in log-binomial regression.

Birth outcomes other than major congenital malformations

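### Section 8.2.2 applies the teratogen and chromosomal exclusions to the whole study, so some users are removed before drug use is counted, and the general-population label on the contextual malformation prevalence cannot hold

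*Protocol*

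**What the plan says.** Section 8.2.2 of the protocol opens with "Patients meeting any of the following criteria will not be included in the study" and lists two criteria: "Pregnancies with exposure to known teratogenic medications during the first trimester" and "Pregnancies carrying a foetus with a chromosomal abnormality diagnosis". Section 8.3.1 fixes the window for the first criterion: "First trimester: from the first day of the last menstrual period (LMP)-90 days to LMP+97 days (both dates inclusive".

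The first primary objective is descriptive. The Abstract asks for use of the three drugs "overall (as used in women for any therapeutic use", and "as both overall and in the subcategory of monotherapy (no concomitant administration with other antiepileptic drugs AEDs". Section 7 defines the measure as "Prevalence of use (proportion of pregnancies with 1 or more dispensing of a given drug". Section 6 says the pattern of use will be evaluated in all pregnancies identifiable from the registries, and Section 8.2 defines the study population as all pregnancies identified in the stated years.

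For the contextual malformation figure, Section 8.7.4.1 promises: "In addition overall prevalence of malformations in the whole general population will be presented". Section 7 places the same figure in the total population of live or stillborn children. Section 8.3.2.4 places it in the total study population.

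**The concern.** Both exclusions are reasonable when the question is whether pregabalin is associated with malformations. They are written, however, as entry criteria for the study, and the study also has a drug-utilisation objective that ranks as primary.

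A woman dispensed pregabalin, lamotrigine or duloxetine who also had a known teratogen dispensed between LMP-90 and LMP+97 would never reach the use tables. Because the window opens 90 days before the LMP, this includes a woman whose only teratogen dispensing was before conception, and she is lost from the second- and third-trimester tables as well. A pregnancy with a foetal chromosomal diagnosis is lost too, although that diagnosis has no bearing on whether a drug was dispensed.

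At stake is whether the use figures given to the regulator describe use in pregnancy or use in a selected subset, and whether the contextual malformation prevalence is what its label says.

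**Working it through.** The protocol states no figure for how many pregnancies the exclusions remove, so there is nothing to reproduce. The check is a comparison of text, followed by arithmetic on stated assumptions.

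**1. Scope.** The authors write analysis-specific exclusions where they want them: Section 8.3.1 removes pregnancies exposed to both pregabalin and lamotrigine only from analyses with lamotrigine as comparator, and does the same for duloxetine. Section 8.2.2 has no such limit, so its plain reading is study-wide.

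**2. Who is removed.** Neither criterion mentions polytherapy. Under Section 8.3.1 one dispensing is enough for exposure, whatever else is dispensed, and monotherapy is a separate subset. Use of AEDs is a covariate in Section 8.3.3. Only users who also had a known teratogen in the window, or a foetal chromosomal diagnosis, are lost.

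**3. Number and prevalence of users.** Inputs from Table 4, taken here as counts before exclusions (the table does not say):
- pregnancies: 730,000 + 580,000 + 650,000 + 800,000 = 2,760,000
- first-trimester pregabalin: 200 + 700 + 200 + 400 = 1,500
- prevalence: 1,500 / 2,760,000 = 54.3 per 100,000

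Let f be the share of users, and g the share of all pregnancies, with a first-trimester teratogen (both assumed). Prevalence after exclusion = 1,500(1 − f) / [2,760,000(1 − g)].

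| f | g | users left | per 100,000 | relative change |
|---|---|---|---|---|
| 2% | 2% | 1,470 | 54.3 | 0% |
| 5% | 0.5% | 1,425 | 51.9 | −4.5% |
| 10% | 0.5% | 1,350 | 49.2 | −9.5% |
| 20% | 0.1% | 1,200 | 43.5 | −19.9% |

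The count of users falls in every row. The prevalence falls only when f exceeds g.

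**4. Monotherapy share.** Assume 80 of 100 users are on monotherapy.
- If all those removed are AED combination users: removing 2 gives 80/98 = 81.6%; removing 10 gives 80/90 = 88.9%. Combination users are then 18.4% and 11.1%, so they are depleted and not eliminated.
- If all 10 removed are monotherapy users with a non-AED teratogen: 70/90 = 77.8%.

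The share can therefore move either way.

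**5. Which drug is more affected.** If the teratogen list includes other AEDs, loss falls on combination users. In Table 1, epilepsy is 79% of 675 identifiable first-trimester indications for lamotrigine (0.79 × 675 ≈ 533) and 4% of 74 for pregabalin (0.04 × 74 ≈ 3). The effect would then be expected to be larger for lamotrigine, which belongs to the same objective.

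**6. Contextual malformation prevalence.** Section 8.5 uses a background of 3%.
- Teratogen exclusion, with assumed risk ratio RR: 0.03 / (1 − g + g·RR). With g = 0.1% and RR = 1.5 this is 2.999%; with g = 2% and RR = 3 it is 2.885%.
- Chromosomal exclusion, if the 3% includes such cases and they are an assumed share c of it: 0.03(1 − c) / (1 − 0.03c). With c = 5% this is 2.85%; with c = 15% it is 2.56%.

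Of the three population names used for this figure, only the total study population in Section 8.3.2.4 fits data to which Section 8.2.2 has been applied.

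**The case against.** The best defence is that inclusion and exclusion criteria together define a study population, and describing use in an openly restricted population is legitimate. Section 7 speaks of pregnancies ending in live or stillbirths without adding the word all. Figure 1 (the population flow) and the Annex 3 code lists and table shells are not in the text available, and may name the teratogens or apply the exclusions at a later step. For the contextual prevalence, using the same exclusions as the exposure groups makes the comparison cleaner.

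Part of this stands. Keeping the exclusions for the contextual figure is defensible, and then only the label is wrong. If Figure 1 or Annex 3 applies the exclusions later, the remedy is wording alone. But Section 8.2.2 would still say otherwise, and the Abstract and Section 6 describe use for any therapeutic purpose in all identifiable pregnancies, which a study-wide exclusion does not deliver.

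A reader might infer something stronger: that the use figures are stripped of polytherapy users, so that the monotherapy share is overstated and the epilepsy share understated. The document does not support that. Other polytherapy stays in, no teratogen is named, and non-AED teratogens would remove monotherapy users as well. Section 8.7.4.1 also promises a number and proportion on monotherapy without saying that users are the denominator.

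**Conclusion.** The point holds as a conflict between a stated eligibility rule and a stated primary objective, together with an inconsistent label for the contextual malformation prevalence. As written, the number of users is understated by however many meet either criterion. Prevalence of use is understated if users are dispensed known teratogens more often than pregnant women in general. On the assumptions shown, the change for first-trimester pregabalin runs from none to about −20%; none of those inputs comes from the protocol. Selective depletion of combination users, greater for lamotrigine than for pregabalin, follows only if the teratogen list includes other AEDs. Neither the size of the effect nor its direction for the monotherapy share can be determined from the document. The association analyses are not affected. The correction should be made because it bears on a primary objective and is cheap.

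**What to change.** Reword Section 8.2.2 so that both exclusions apply to the association analyses only, and run the drug-utilisation tables on all registered pregnancies ending in live or stillbirth. For the contextual malformation prevalence, choose one of two routes: compute it in all births, or keep the exclusions for comparability and label it as the restricted study population. Use the chosen term alike in Sections 7, 8.3.2.4 and 8.7.4.1. Report the number removed by each criterion in each exposure group, so that a reader can judge the effect.

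The cost is one extra population flag, some protocol wording, and descriptive denominators that differ from those of the comparative analyses, which a table footnote can explain. No new data are needed and the comparative estimates do not change.

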8.3. Variables

8.3.1. Exposures

For the purposes of timing of exposure, trimesters of pregnancy will be defined as follows:

- First trimester: from the first day of the last menstrual period (LMP)-90 days to LMP+97 days (both dates inclusive);
- Second trimester: from LMP+98 days to LMP+202 days (both dates inclusive);
- Third trimester: from LMP+203 days (inclusive) until pregnancy end date (not included).

Exposure during the first trimester

Pregabalin exposure during the first trimester will be defined as at least one maternal dispensing of pregabalin during the first trimester. Pregabalin monotherapy in the first trimester will be defined as first-trimester exposure to pregabalin and no first-trimester dispensing for any other AED.

Comparators:

Unexposed to pregabalin during the first trimester comparator is defined as pregnancies without a dispensing for pregabalin or any other AED, including lamotrigine or duloxetine, during the first trimester.

Lamotrigine exposure in the first trimester is defined by at least one dispensing of lamotrigine during the first trimester. Lamotrigine monotherapy in the first trimester will be defined as first-trimester exposure to lamotrigine and no first-trimester dispensing for any other AED.

Duloxetine exposure in the first trimester is defined by at least one dispensing of duloxetine during the first trimester. Duloxetine monotherapy in the first trimester will be defined as first-trimester exposure to duloxetine and no first-trimester dispensing for any AED.

Lamotrigine or duloxetine exposure in the first trimester is defined by at least one dispensing of lamotrigine or duloxetine or both during the first trimester. Lamotrigine or duloxetine monotherapy in the first trimester will be defined as first-trimester dispensing of lamotrigine or duloxetine or both and no first-trimester dispensing for any other AED.

For analyses that use lamotrigine as the comparator, pregnancies exposed to both pregabalin and lamotrigine in the first trimester will be excluded. For analyses that use duloxetine as the comparator, pregnancies exposed to both pregabalin and duloxetine in the first trimester will be excluded.

Exposure any time during pregnancy

Pregabalin exposure any time during pregnancy is defined by at least one dispensing of pregabalin during any trimester. Pregabalin monotherapy any time during pregnancy will be defined as any-pregnancy exposure to pregabalin and no dispensing for any other AED during any trimester.

Comparators:

Unexposed to pregabalin during any trimester comparator is defined as pregnancies without dispensing for pregabalin or other AEDs including lamotrigine, or duloxetine during any trimester.

Lamotrigine exposure any time during pregnancy is defined by at least one dispensing of lamotrigine during any trimester. Lamotrigine monotherapy any time during pregnancy will be defined as any-pregnancy exposure to lamotrigine and no dispensing for any other AED during any trimester.

Duloxetine exposure any time during pregnancy is defined by at least one dispensing of duloxetine during any trimester. Duloxetine monotherapy any time during pregnancy will be defined as any-pregnancy exposure to duloxetine and no dispensing for any AED during any trimester.

Lamotrigine or duloxetine exposure any time during pregnancy defined by at least one dispensing of lamotrigine or duloxetine or both during any trimester. Lamotrigine or duloxetine monotherapy any time during pregnancy will be defined as any-pregnancy exposure to lamotrigine or duloxetine or both and no dispensing for any other AED during any trimester.

For analyses that use lamotrigine as the comparator pregnancies exposed to both pregabalin and lamotrigine in any trimester will be excluded. For analyses that use duloxetine as the comparator pregnancies exposed to both pregabalin and duloxetine in any trimester will be excluded.

In a sensitivity analysis, monotherapy with pregabalin, lamotrigine, and/or duloxetine will be defined by absence of other AED, selective serotonin reuptake inhibitors, or benzodiazepines.

